5.2 SAFETY PARAMETERS AND DEFINITIONS

Safety assessments will consist of monitoring and recording adverse events, including SAEs and adverse events of special interest, performing protocol-specified safety laboratory assessments, measuring protocol-specified vital signs, and conducting other protocol-specified tests that are deemed critical to the safety evaluation of the study.

Certain types of events require immediate reporting to the Sponsor, as outlined in Section 5.4.

5.2.1 Adverse Events

According to the ICH guideline for GCP, an adverse event is any untoward medical occurrence in a clinical investigation subject administered a pharmaceutical product, regardless of causal attribution. An adverse event can therefore be any of the following:

- Any unfavorable and unintended sign (including an abnormal laboratory finding), symptom, or disease temporally associated with the use of a medicinal product, whether or not considered related to the medicinal product

- Any new disease or exacerbation of an existing disease (a worsening in the character, frequency, or severity of a known condition), except as described in Section 5.3.5.10
- Recurrence of an intermittent medical condition (e.g., headache) not present at baseline
- Any deterioration in a laboratory value or other clinical test (e.g., ECG, X-ray) that is associated with symptoms or leads to a change in study treatment or concomitant treatment or discontinuation from study treatment
- Adverse events that are related to a protocol-mandated intervention, including those that occur prior to assignment of study treatment (e.g., screening invasive procedures such as biopsies)

5.2.2 Serious Adverse Events (Immediately Reportable to the Sponsor)

A SAE is any adverse event that meets any of the following criteria:

- Is fatal (i.e., the adverse event actually causes or leads to death)
- Is life threatening (i.e., the adverse event, in the view of the investigator, places the patient at immediate risk of death)

This does not include any adverse event that had it occurred in a more severe form or was allowed to continue might have caused death.

- Requires or prolongs in-patient hospitalization (see Section 5.3.5.11)
- Results in persistent or significant disability/incapacity (i.e., the adverse event results in substantial disruption of the patient's ability to conduct normal life functions)
- Is a congenital anomaly/birth defect in a neonate/infant born to a mother exposed to study treatment
- Is a significant medical event in the investigator's judgment (e.g., may jeopardize the patient or may require medical/surgical intervention to prevent one of the outcomes listed above)

The terms "severe" and "serious" are not synonymous. Severity refers to the intensity of an adverse event (e.g., rated as mild, moderate, or severe, or according to NCI CTCAE; see Section 5.3.3); the event itself may be of relatively minor medical significance (such as severe headache without any further findings).

Severity and seriousness need to be independently assessed for each adverse event recorded on the eCRF.

The SAEs are required to be reported by the investigator to the Sponsor immediately (i.e., no more than 24 hours after learning of the event; see Section 5.4.2 for reporting instructions).

5.2.3 Adverse Events of Special Interest (Immediately Reportable to the Sponsor)

Adverse events of special interest are required to be reported by the investigator to the Sponsor immediately (i.e., no more than 24 hours after learning of the event; see Section 5.4.2 for reporting instructions). Adverse events of special interest for this study include the adverse events of special interest listed below.

Adverse events of special interest to any study drug are as follows:

- Cases of potential drug-induced liver injury that include an elevated ALT or AST in combination with either an elevated bilirubin or clinical jaundice, as defined by Hy's law (see Section 5.3.5.7)
- Suspected transmission of an infectious agent by the study treatment, as defined below

Any organism, virus, or infectious particle (e.g., prion protein transmitting transmissible spongiform encephalopathy), pathogenic or non-pathogenic, is considered an infectious agent. A transmission of an infectious agent may be suspected from clinical symptoms or laboratory findings that indicate an infection in a patient exposed to a medicinal product. This term applies only when a contamination of any of the study treatment components is suspected.

Adverse events of special interest to obinutuzumab are as follows:

- TLS of any grade of severity, and irrespective of causality
- Second malignancies

Adverse events of special interest to atezolizumab are as follows:

- Pneumonitis
- Colitis
- Endocrinopathies: diabetes mellitus, pancreatitis, adrenal insufficiency, hyperthyroidism, and hypophysitis
- Hepatitis, including AST or ALT > 10 x ULN
- Systemic lupus erythematosus
- Neurological disorders: Guillain-Barré syndrome, myasthenic syndrome or myasthenia gravis, and meningoencephalitis
- Events suggestive of hypersensitivity, infusion-related reactions, cytokine-release syndrome, influenza-like illness, systemic inflammatory response syndrome, and systemic immune activation
- Nephritis
- Ocular toxicities (e.g., uveitis, retinitis)
- Myositis

- Myopathies, including rhabdomyolysis
- Grade ≥ 2 cardiac disorders (e.g., atrial fibrillation, myocarditis, pericarditis)
- Vasculitis

5.2.4 Dose-Limiting Toxicities (Immediately Reportable to the Sponsor)

During the DLT assessment window (Cycles 1 and 2), adverse events identified as DLTs, as defined in Section 3.1.2.1.1, are required to be reported by the investigator to the Sponsor immediately (i.e., no more than 24 hours after learning of the event; see Section 5.4.2 for reporting instructions).

5.2.5 Selected Adverse Events

Adverse events of special interest are listed in Section 5.2.3. Selected adverse events in this study are defined as adverse events for which additional data collection or analyses will be performed. Selected adverse events do not require immediate reporting if they are not serious (except for TLS and second malignancies).

The following adverse events are considered selected adverse events:

- Thrombocytopenia, including acute thrombocytopenia (events occurring during and within 24 hours following obinutuzumab infusion)
- Hepatitis B reactivation
- Cardiac events
- IRRs
- All infections, including PML
- Neutropenia, including prolonged neutropenia (neutropenia < 1000 cells/ μ L that does not resolve after 28 days without obinutuzumab treatment) and late-onset neutropenia (neutropenia < 1000 cells/ μ L occurring ≥ 28 days after obinutuzumab treatment has been completed or stopped)
- GI perforation
- Peripheral neuropathy (motor and/or sensory)

Events for which additional data collection will be required are PML, Hepatitis B and Hepatitis B reactivation.

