5.1.2.5 Neutropenia

Neutropenia is very common in patients receiving rituximab (occurring in $\geq 10\%$ of patients) based on clinical trial experience. However, delayed onset neutropenia is very rare (occurring in < 1 of 10,000 patients), and the incidence of prolonged neutropenia is unknown. Neutropenia may lead to serious or overwhelming infection, especially if profound (Grade 3–4), prolonged, associated with breaches in natural mucosal barriers (e.g., diarrhea and/or mucositis), and/or other immunological defects (e.g., lymphopenia, hypogammaglobulinemia, and acquired immunodeficiency syndrome). Despite an increase in incidence of neutropenia and Grade 3–4 neutropenia associated with rituximab, most studies have not reported a significant increase in serious neutropenic infections.

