5.1.5 Risk of Overlapping Toxicities and Drug-Drug Interactions

As with any experimental regimen, there is a risk of unexpected/unknown toxicities that may occur during the study. Two patients with RR FL treated with obinutuzumab, atezolizumab, and polatuzumab vedotin experienced the concomitant occurrence of severe and difficult-to-treat dermatitis, oral mucositis, and ocular events refractory to standard treatment with corticosteroids. The severity and the concomitant observation of this constellation of events is not consistent with the safety profile of the individual drugs (see Section 5.1.6), and hence constitutes an unexpected safety signal.

Hematologic toxicity (mainly neutropenia) is the most common toxicity associated with obinutuzumab, rituximab, and polatuzumab vedotin. The risk of overlapping hematologic toxicity with the addition of atezolizumab to obinutuzumab/rituximab and polatuzumab vedotin is expected to be low. There is no expectation for the combination to enhance the risk of peripheral sensory neuropathy associated with polatuzumab vedotin. Considering the risk associated with each individual component of the combination (Section 5.1.1, Section 5.1.3, and Section 5.1.4), the expected overlapping non-hematologic toxicities are IRRs, infections, skin rash, GI toxicity, and hepatotoxicity/elevated liver transaminases. Additionally, there is an identified risk of TLS with obinutuzumab and rituximab and a potential risk with polatuzumab vedotin because these agents can result in the rapid destruction of a large number of tumor cells. Therefore, overlapping toxicity in regard to TLS cannot be excluded. Guidelines for management of patients who develop TLS are provided in [Table 14](#).

The risk of clinically relevant PK DDIs is low between obinutuzumab/rituximab, atezolizumab, and polatuzumab vedotin. Obinutuzumab/rituximab and polatuzumab vedotin are known to deplete or decrease circulating B cells and tumor burden, which may potentially affect the target-mediated clearance of obinutuzumab and polatuzumab vedotin. However, in relapsed or refractory FL and DLBCL, the baseline B-cell count is low; therefore, the likelihood of B-cell–mediated pharmacokinetic DDI is relatively low. This hypothesis is supported by preliminary results from the ongoing Study GO27834 in relapsed or refractory FL and DLBCL, where no interaction was observed between polatuzumab vedotin and rituximab.

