6.5 SAFETY ANALYSES

The safety analyses will be performed by treatment group, separately for each study phase (i.e., dose-escalation and expansion). The main analysis for safety will include data until end of study. Additionally, a censoring will be applied as of 1 March 2018 to the safety analyses, to evaluate the effect of the triplet drug combination in each treatment group. The sensitivity analysis will be based on the censored safety dataset and will include data from patients as of 1 March 2018 plus the 90-day safety reporting window (see Section 5.3.1). Patients enrolled and who have not received any treatment with atezolizumab will be analyzed separately by treatment group, G +Pola and R +Pola.

Safety will be assessed through summaries of adverse events, changes from baseline in laboratory test results, and laboratory data with values outside of the normal ranges.

All adverse events occurring on or after the first dose of study treatment will be summarized by mapped term, appropriate thesaurus levels, and NCI CTCAE v4.0 grade. All SAEs, adverse events of special interest, and selected adverse events will be summarized and listed.

Deaths reported during the treatment period and during post-treatment follow-up will be listed.

Relevant laboratory results will be displayed by time, with Grade 3 and 4 values identified as appropriate.

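### Three selected-event sub-categories are timed from obinutuzumab only, so they do not fit the 23 DLBCL patients, who receive rituximab

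*Combined protocol and SAP*

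**What the plan says.** Section 5.2.5 lists the selected adverse events for the whole study without splitting them by drug. Two entries carry sub-categories with their own timing rule:

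- Acute thrombocytopenia: events "occurring during and within 24 hours following obinutuzumab infusion".
- Prolonged neutropenia: a count below 1000 cells/µL "that does not resolve after 28 days without obinutuzumab treatment".
- Late-onset neutropenia: a count below 1000 cells/µL at least 28 "days after obinutuzumab treatment has been completed or stopped".

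Section 5.1.1.4 repeats the two neutropenia definitions among the obinutuzumab risks. No section gives a version for rituximab or for study treatment in general.

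DLBCL patients are treated with rituximab and polatuzumab vedotin (Sections 3.1.3.1 and 4.3.2.5). Section 1.2.2.3 records that Version 4 stopped the use of obinutuzumab in DLBCL. Section 6.5 runs the safety analyses by treatment group and states: "All SAEs, adverse events of special interest, and selected adverse events will be summarized and listed". Section 5.1.2 includes prolonged neutropenia among the rituximab risks. Section 5.1.2.5 mentions delayed-onset neutropenia and adds that "the incidence of prolonged neutropenia is unknown".

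**The concern.** A sub-category needs a reference time that exists for the patient being classified. For DLBCL patients it does not exist, yet the plan calls for a selected-event output in their group. If the sub-categories are programmed as written, a zero in the DLBCL column could come from the definition and be read as an observation. A prolonged neutropenia count could include episodes that arose and persisted while treatment continued, although the term is meant for failure to recover off the antibody. The gap matters most for the two neutropenia categories, because the protocol itself names prolonged and delayed-onset neutropenia under rituximab and says that the frequency of the first is not known.

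**Working it through.** **Step 1: patients concerned.** Section 6.1 gives 13 FL and 23 DLBCL patients as of 1 March 2018, when enrollment stopped. The total is not printed: 13 + 23 = 36. DLBCL share: 23/36 = 63.9%. FL share, where the definitions work: 13/36 = 36.1%.

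**Step 2: each definition applied to a patient with no obinutuzumab dose.**

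| Sub-category | Reference time in 5.2.5 | Literal result in DLBCL |
|---|---|---|
| Acute thrombocytopenia | an obinutuzumab infusion | can never be met |
| Late-onset neutropenia | end of obinutuzumab | can never be met |
| Prolonged neutropenia | 28 days without obinutuzumab | not evaluable if prior obinutuzumab is presupposed; otherwise the condition always holds, and any neutropenia below 1000 cells/µL unresolved after 28 days qualifies |

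**Step 3: the permissive reading of prolonged neutropenia.** Induction cycles last 21 days in both groups. In an FL patient dosed on schedule during induction, obinutuzumab is never absent for 28 days (21 < 28), so neutropenia in that period does not qualify. In a DLBCL patient, a 28-day stretch within Cycles 1–6 contains at least one Day 1 of rituximab and polatuzumab vedotin (28 > 21) and still qualifies. The same course would be classified differently in the two groups.

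**Step 4: what a printed zero would suggest.** The protocol plans no interval for safety counts, so this is illustrative. For a true 0 of 23, the exact (Clopper-Pearson) upper limit is

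- two-sided 90%: 1 − 0.05^(1/23) = 12.2%
- two-sided 95%: 1 − 0.025^(1/23) = 14.8%

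A zero that follows from the definition supports neither bound.

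**Step 5: can existing data support a rituximab reference time?** Section 5.3.1 collects all adverse events to 90 days after the last dose, and Section 6.3 lists dosing data. Appendix 2 places the end-of-induction (EOI) assessments, which include hematology, 6–8 weeks (42–56 days) after Day 1 of the last induction cycle. That is 42 − 28 = 14 to 56 − 28 = 28 days past the 28-day mark. Patients who stop early because of an adverse event may be assessed 4–8 weeks (28–56 days) after their last dose, which at the early end only just reaches the mark. As the table reads in the available text, no hematology is scheduled at the 90-day visit in DLBCL.

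**The case against.** Several points on the other side are sound.

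- **The parent terms have no drug restriction.** Every neutropenia and thrombocytopenia in DLBCL is a selected event, and Section 6.5 also summarizes all adverse events by grade and displays laboratory results by time. A reader might infer that such events go uncounted in DLBCL; they do not.
- **Section 6.5 does not commit to tabulating the sub-categories.** The consequence is therefore conditional on their being reported. But Section 5.2.5 describes selected events as those singled out for extra data or analysis, so such an output is a fair expectation.
- **Prolonged neutropenia can equally be read as not applicable without prior obinutuzumab.** That stands. Two defensible readings with opposite results are still a reason to fix the text.
- **Acute thrombocytopenia is absent from the rituximab risk list in Section 5.1.2,** so its obinutuzumab reference may be deliberate. Section 5.2.5 does not say so, whereas Section 5.2.3 labels its events by drug.
- **Few late-onset events may be expected.** Section 5.1.2.5 puts delayed-onset neutropenia with rituximab below 1 in 10,000: 23 × 0.0001 = 0.0023 expected events at most. That rate describes rituximab. Polatuzumab vedotin, for which neutropenia is an identified risk (Section 5.1.4.1), is given as well. A low expected count should still come from the data.
- **No comparison of the rituximab and obinutuzumab groups is planned.** The groups are not randomized, have different diseases and, in FL, include maintenance. A reader might infer that the tables would establish a false safety difference between antibodies; the plan contains no such analysis.
- **Tumor lysis syndrome is a different matter.** Section 5.2.3 puts it under "Adverse events of special interest to obinutuzumab are as follows", while Section 5.1.5 says that "there is an identified risk of TLS with obinutuzumab and rituximab and a potential risk with polatuzumab vedotin". It is tempting to count this as the same error. But it has no obinutuzumab-based timing, and Section 5.2.5 excepts it from the non-immediate reporting rule without limiting this to one drug. It needs clarification only.

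**Conclusion.** The point holds for the three sub-categories in the DLBCL group. As written, two cannot be met there and the third is either not evaluable or too easily met. The definitions do not fit 23 of 36 enrolled patients (63.9%). A reader might take that figure as the number of misclassified patients or events. The documents give no event counts, so that number is unknown and could be zero.

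The primary endpoint, overall adverse event rates and all FL results are untouched. The case is strongest for prolonged and late-onset neutropenia and weaker for acute thrombocytopenia. It assumes that all 23 DLBCL patients received rituximab and none received obinutuzumab. The documents describe DLBCL enrollment this way and report no exception, although versions before Version 4 foresaw obinutuzumab in DLBCL. That the wording was simply not updated at that change is plausible but not shown.

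**What to change.** In Section 5.2.5, time prolonged and late-onset neutropenia from the last dose of the anti-CD20 antibody that the patient received, obinutuzumab or rituximab as applicable. For acute thrombocytopenia, either do the same or state that the sub-category applies to obinutuzumab only and print not applicable instead of 0 in the DLBCL output.

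The cost is a wording change and one altered derivation in the safety programs, using dosing dates and adverse events already collected. With this change the two neutropenia sub-categories could be classified in 36 of 36 patients instead of 13 of 36.

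Two limits should be stated with the results. Late-onset neutropenia in DLBCL will rest mainly on the EOI sample and reported adverse events. An antibody-based reference time also takes no account of when polatuzumab vedotin was last given, which is equally true of the present FL definition.

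Separately, reconcile Sections 5.1.5, 5.2.3 and 5.2.5 on whether tumor lysis syndrome is an event of special interest in rituximab-treated patients.

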5.3 METHODS AND TIMING FOR CAPTURING AND ASSESSING SAFETY PARAMETERS

The investigator is responsible for ensuring that all adverse events (see Section 5.2.1 for definition) are recorded on the Adverse Event eCRF and reported to the Sponsor in accordance with instructions provided in this section and in Sections 5.4–5.6.

For each adverse event recorded on the Adverse Event eCRF, the investigator will make an assessment of seriousness (see Section 5.2.2 for seriousness criteria), severity (see Section 5.3.3), and causality (see Section 5.3.4).

5.3.1 Adverse Event Reporting Period

Investigators will seek information on adverse events at each patient contact. All adverse events, whether reported by the patient or noted by study personnel, will be recorded in the patient's medical record and on the Adverse Event eCRF.

After informed consent has been obtained **but prior to initiation of study treatment**, only SAEs caused by a protocol-mandated intervention (e.g., invasive procedures such as biopsies, discontinuation of medications) should be reported (see Section 5.4.2 for instructions for reporting SAEs).

After initiation of study treatment, all adverse events will be reported until 90 days after the last dose of study treatment. After this period, the investigator should report any SAEs that are believed to be related to prior study treatment (see Section 5.6).

An exception is made for Grade 3 or 4 infections (related and unrelated to study treatment), which should be reported until up to 2 years after the last dose of obinutuzumab (G+Atezo+ Pola treatment group).

Similarly, second malignancies (related and unrelated to study treatment) will be reported indefinitely (even if the study has been closed) for patients who received obinutuzumab (see Section 5.6).

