3.2 END OF STUDY AND LENGTH OF STUDY

The end of this study is defined as the time when all enrolled patients with FL and all enrolled patients with DLBCL have completed the 90-day safety follow-up visit, following completion or premature discontinuation of study treatment.

The total length of the study, from screening of the first patient to the end of the study, is expected to be approximately 4 years.

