5.1.1.6 Infections

On the basis of its mechanism of action, resulting in profound B-cell depletion, obinutuzumab may be associated with an increased risk of infections. Obinutuzumab should not be administered to patients with active infection, and caution should be exercised when including patients with a history of recurrent or chronic infections.

Serious bacterial, fungal, and new or reactivated viral infections can occur during and following the completion of obinutuzumab therapy. Fatal infections have been reported.

In the Gallium study (BO21223), a high incidence of infections was observed in all phases of the study (81%), including follow-up (19%), with the highest incidence observed during maintenance (70%) in recipients of obinutuzumab and chemotherapy. During the follow-up phase, Grade 3–5 infections (12%) were observed more in patients who received obinutuzumab plus bendamustine in the induction phase.

Reactivation of hepatitis B in patients with chronic hepatitis (HBsAg positive) with evidence of prior hepatitis B exposure or in patients who are carriers (HBsAg negative and HBcAb positive) has been reported with other anti-CD20 antibodies. The risk is increased particularly when anti-CD20 antibodies are administered with immunosuppressive therapies, such as steroids or chemotherapy. Patients who are positive for HBsAg and HBcAb are not eligible for this study.

JC viral infection resulting in PML has been reported in patients treated with obinutuzumab. The diagnosis of PML should be considered in any patient presenting with new-onset neurologic manifestations. The symptoms of PML are unspecific and can vary depending on the affected region of the brain. Motor symptoms with corticospinal tract findings (e.g., muscular weakness, paralysis, and sensory disturbances), sensory abnormalities, cerebellar symptoms, and visual field defects are common. Some signs or symptoms regarded as "cortical" (e.g., aphasia or visual-spatial disorientation) may occur. Evaluation of PML includes, but is not limited to, consultation with a neurologist, brain MRI, and lumbar puncture (cerebrospinal fluid testing for JC viral DNA). Additional guidelines for medical management of PML in this study are provided in Section 5.1.6.

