5.6 ADVERSE EVENTS THAT OCCUR AFTER THE ADVERSE EVENT REPORTING PERIOD

After the end of the adverse event reporting period (defined as 90 days after the last dose of study treatment), all deaths, regardless of cause, should be reported through use of the Long-Term Survival Follow-Up eCRF.

In addition, if the investigator becomes aware of a serious adverse event that is believed to be related to prior exposure to study drug, the event should be reported through use of the Adverse Event eCRF.

An exception is made for Grade 3 and 4 infections (related and unrelated to prior study treatment), which should be reported until up to 2 years after the last dose of study treatment.

The Sponsor should also be notified of events of second malignancies indefinitely (related and unrelated to study treatment, even if the G+Atezo+pol treatment group or the overall study has been closed) for patients who received obinutuzumab.

If the EDC system is not available, the investigator should report these events directly to the Sponsor or its designee, either by faxing or by scanning and emailing the paper

Clinical Trial Serious Adverse Event/Adverse Event of Special Interest Reporting Form using the fax number or email address provided to investigators.

**5.7 EXPEDITED REPORTING TO HEALTH AUTHORITIES,
INVESTIGATORS, INSTITUTIONAL REVIEW BOARDS, AND
ETHICS COMMITTEES**

The Sponsor will promptly evaluate all SAEs and adverse events of special interest against cumulative product experience to identify and expeditiously communicate possible new safety findings to investigators, IRBs, ECs, and applicable health authorities based on applicable legislation.

To determine reporting requirements for single adverse event cases, the Sponsor will assess the expectedness of these events using the following reference document:

- Obinutuzumab Investigator's Brochure
- Atezolizumab Investigator's Brochure
- Polatuzumab Vedotin Investigator's Brochure
- Rituximab Investigator's Brochure

The Sponsor will compare the severity of each event and the cumulative event frequency reported for the study with the severity and frequency reported in the applicable reference document.

Reporting requirements will also be based on the investigator's assessment of causality and seriousness, with allowance for upgrading by the Sponsor as needed.

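### The 2-year late-infection rule omits Grade 5, so fatal late infections judged unrelated may be recorded only as deaths, and for late-finishing FL patients most of the window falls after the end of study

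*Combined protocol and SAP*

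**What the plan says.** **General rule.** Section 5.3.1 states that "all adverse events will be reported until 90 days after the last dose of study treatment". Beyond that, "After this period, the investigator should report any SAEs that are believed to be related to prior study treatment". Section 5.6 puts those related SAEs on the Adverse Event eCRF.

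**Infection exception.** Section 5.3.1 makes an exception for "Grade 3 or 4 infections (related and unrelated to study treatment), which should be reported until up to 2 years" after the last obinutuzumab dose, in the FL group. Appendix 1 footnote aa has the same grades and anchor. Section 5.6 has the same grades but a different anchor: "which should be reported until up to 2 years after the last dose of study treatment".

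**Late deaths.** After the 90 days, Section 5.6 says "all deaths, regardless of cause, should be reported through use of the Long-Term Survival Follow-Up eCRF".

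**Second malignancies.** For patients who received obinutuzumab, Section 5.3.1 says "second malignancies (related and unrelated to study treatment) will be reported indefinitely (even if the study has been closed"). The infection exception has no such words.

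**End of study.** Under Section 3.2 the study ends when all FL patients and "all enrolled patients with DLBCL have completed the 90-day safety follow-up visit". Section 8.5, Appendix 1 footnote kk and Appendix 2 footnote ee define it differently: FL patients off treatment, and DLBCL patients followed for at least 1 year after treatment.

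**Analysis.** Section 5.2.5 makes all infections selected adverse events. Section 6.5 summarises and lists selected adverse events, only lists deaths, and runs the main safety analysis to the end of study.

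**The concern.** The exception is written to apply whatever the causality judgement, so that late infections after obinutuzumab are counted without depending on attribution. Leaving out Grade 5 brings attribution back for the fatal cases. Section 5.1.1.6 acknowledges that fatal infections have occurred with obinutuzumab, and the late-infection figure it cites includes them: "During the follow-up phase, Grade 3–5 infections (12%) were observed more in patients who received obinutuzumab plus bendamustine". A rule that counts a survived Grade 4 infection at month 6 but can miss a fatal one at the same time is the wrong way round.

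The second issue is duration. A 2-year window is promised in a study that may close 90 days after the last patient stops. Sites told expressly to go on reporting second malignancies after closure, and told nothing about infections, may reasonably stop. What is at stake is how complete the descriptive late-infection data are in a group of 13 FL patients. No hypothesis test is involved.

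**Working it through.** The plan gives no figure of its own to reproduce here. The check is a comparison of rules followed by window arithmetic.

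**1. Where a late infection is recorded (day 91 to 2 years, obinutuzumab patient)**

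| Infection | Judged related | Judged unrelated |
|---|---|---|
| Grade 3 or 4, survived | Adverse Event eCRF | Adverse Event eCRF, under the exception |
| First recorded at Grade 3 or 4, then fatal | Adverse Event eCRF, worst grade kept (5.3.5.4), plus survival form | The same |
| First known as fatal | Adverse Event eCRF as a related SAE, plus survival form | Survival form only |

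Table 16 in Section 5.3.3 treats Grade 5 as a separate grade (death) and makes Grade 5 events SAEs, so the related-SAE rule does reach them. Only the bottom right cell is a gap. Within the first 90 days it is closed: Section 5.3.5.8 requires any death not attributed solely to lymphoma to be entered on the Adverse Event eCRF with its cause. For later deaths that section defers to 5.6, which gives no instruction on cause.

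**2. How much of the window the study covers**

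Inputs: a 2-year window of 730 days; a 90-day visit (3.2); 21-day cycles; maintenance starting 8 weeks after Day 1 of Cycle 6; obinutuzumab every second month over 24 months, with 1 month = 28 days (Table 2).

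- Last patient to finish: 90/730 = 12.3% covered. Uncovered: 730 − 90 = 640 days, or 640/30.44 ≈ 21 months.
- Cycle 6 Day 1: 5 × 21 = day 105. Maintenance Month 1: 105 + 56 = day 161. Last dose, Month 23: 161 + 22 × 28 = day 777. Study end if this patient is last: 777 + 90 = day 867.
- Days covered for another patient = 867 + (days by which that patient started earlier) − (study day of last dose).

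| FL patient | Days covered | Share of 730 |
|---|---|---|
| Same start, last dose Cycle 6 Day 1 (day 105) | 762 | full |
| Same start, stops mid-maintenance (day 441) | 426 | 58% |
| Completer, same start (the last finisher) | 90 | 12% |
| Completer, started 180 days earlier | 270 | 37% |
| Completer, started 365 days earlier | 455 | 62% |
| Completer, started 594 days earlier | 684 | 94% |

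The 594 days is roughly the earliest start that fits a 4-year study (1461 − 867, ignoring screening). A same-start patient has the full window if the last dose falls by day 867 − 730 = 137. With calendar months the study end moves to day 921 and the pattern is unchanged.

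**3. The other end-of-study definition**

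The version in Section 8.5 and the appendix footnotes requires no follow-up of FL patients after treatment, so it does not guarantee the last FL finisher any more of the window. The scheduled survival follow-up collects survival status and new anti-lymphoma treatment, not infections, and stops at the end of study.

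**The case against.** The strongest reply is that the gap is small. Related fatal infections are captured without a grade limit or end date, worsening infections keep their worst grade, and an unrelated fatal case still appears in the death listing. All of this stands. It confines the grade gap to infections judged unrelated and first known as fatal. It does not close it, because a death listing is not the infection summary and nothing in 5.6 ensures that the survival form names infection as the cause.

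On closure, neither 5.3.1 nor 5.6 says the 2-year duty lapses, and 5.6 gives a direct-to-sponsor route, for use when the EDC system is unavailable, that follows both exceptions. Part of the different wording for second malignancies may also reflect that their reporting is indefinite. That is fair, and makes the second part a missing statement rather than a contradiction. The main safety analysis still stops at the end of study, so late reports would not enter it. The extension study in Section 4.3.4 is for patients who continue study treatment, not for those already in their 2-year window.

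A reader might infer that all fatal late infections go to the survival form, or that patients with the longest exposure always have the shortest follow-up. The documents support neither: the first fails for related and already-recorded events, and the second ignores entry date, as the table shows. A reader might also apply the 12% in Section 5.1.1.6 to the 13 FL patients. That figure concerns obinutuzumab plus bendamustine in another trial and is not split by fatality or relatedness, so it cannot size a loss here.

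**Conclusion.** The point holds in a limited form. As written, the exception can count a survived late infection and miss an unrelated fatal one. For late-finishing FL patients, up to 640 of 730 days lie beyond the Section 3.2 end of study and the safety cutoff, with no statement that infection reporting continues. Earlier finishers have partial or full cover.

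The 640 days is the worst case, for the last patient to stop, and assumes the Section 3.2 definition governs. The intermediate coverage figures assume that the last FL patient completes maintenance on schedule; individual start dates are not in the documents. Under-counting is a risk, not a shown result. Its size cannot be computed, because the documents give no number of fatal late infections by relatedness. Nor does the plan include a formal late-infection rate or comparison that would be biased. This is a cheap improvement to the completeness of the safety data, and does not affect the primary analysis.

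**What to change.** 1. In Sections 5.3.1 and 5.6 and Appendix 1 footnote aa, extend the exception to Grade 3–5 infections, and require a fatal infection to be entered on the Adverse Event eCRF as well as the survival form.
2. State that infection reporting for patients who received obinutuzumab continues to 2 years after the last dose even if the study has closed, using the reporting route already in 5.6. Say how reports received after the Section 6.5 cutoff will be presented.
3. Reconcile the end-of-study definitions: Section 3.2 against Section 8.5, Appendix 1 footnote kk and Appendix 2 footnote ee.
4. Reconcile the 2-year anchors: last obinutuzumab dose in the FL group (5.3.1, footnote aa) against last study treatment with no group restriction (5.6). Appendix 2 footnote w gives DLBCL patients no infection exception, so the intended population should be stated.

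The cost is a few words in three places, two reconciliations, and a small reporting load on sites after closure for at most 13 patients.
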